4.2.3 Sensitivity Analyses

As sensitivity analyses, the same analyses as described in Section 4.2.2 will be performed for the EVAL population and PP population. Also, the same analyses as described in Section 4.2.2 will be performed by imputing creatinine measurements or urine oxalate values reported as '<x' where x is the lower limit of quantification (LLOQ) value.

Similar analyses will be performed for absolute change from baseline at Month 6 and averaged over Month 3 to Month 6 in spot urinary oxalate-to-creatinine ratio for MITT population, EVAL population, and PP population.

To further adjust for the any potential confounding effect of natural maturity on spot urinary oxalate-to-creatinine ratio, similar analyses will be performed on the ratio of spot urinary oxalate-to-creatinine ratio to the ULN tailored to individual patient's age for MITT population, EVAL population, and PP population.

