### 8.1. Efficacy Assessments

#### 8.1.1. Spot Urine Collection

Oxalate is a dicarboxylic acid that is a normal end-product of metabolism. Most oxalate in the body is produced in the liver. Humans lack an enzyme to degrade oxalate, and thus it must be eliminated by the kidney. In individuals with PH, mutations in the *AGXT*, *GRHPR*, or *HOGAI* gene result in the overproduction of oxalate by the liver, which causes increased oxalate excretion by the kidneys.

The primary measurement of oxalate in the urine will be via spot urine collection. The second morning void is thought to offer the least variability in terms of Uox/ creatinine.

Urine samples will be collected for the determination of Uox and creatinine. Six spot urine samples (3 of which must be second morning void) will be collected over a 3-day period during Screening. Baseline is defined as the average of the 6 screening values.

Four on-treatment spot urine samples (2 of which must be second morning void) will be collected over a 2-day period on a monthly basis.

Participants should avoid consuming vitamin C, including multivitamins, in the 24 hours preceding urine collection.

Any participant who prematurely discontinues study intervention should perform 4 spot urine collections as directed by the Medical Monitor.

Complete instructions for the spot urine collection, including in infants, will be provided in the Urine Collections Instructions.

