4.1.1.2 Baseline

For all endpoints (except spot urinary oxalate-to-creatinine ratio and annualized stone events rate), the last non-missing observation recorded prior to the first dose of study intervention will be used as the baseline observation for all calculations of change from baseline.

For assessments where the time is not collected (like QoL questionnaires), the last observation recorded prior or during the day of the first dose will be considered as baseline.

For spot urinary oxalate-to-creatinine ratio (including spot urinary oxalate and creatinine measurements), the average of all available spot urine samples (retest samples will be used if available) collected at screening will be used as baseline value.

For annualized stone events rate, baseline will be the number of stone events observed over the past 12 months prior to screening.

Any measure assessed after the date/time of the first dose will be considered as post baseline assessments.

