4.1.1.3 Handling of Dropouts or Missing Data

4.1.1.3.1 Missing Efficacy Endpoint Data

While all possible efforts will be made to ensure that participants stay in the study and all data is collected as scheduled, the occurrence of missing data cannot be eliminated.

Participants who sign the informed consent form but do not receive the study intervention may be replaced. Should there be a participant(s) who signs the informed consent form, and receives the study intervention and subsequently withdraws, or is withdrawn or discontinued from the study before the Day 180 Visit, an additional participant(s) in the same age group may be enrolled to ensure that an adequate number of participants complete the Day 180 visit assessments.

No other imputation will be used in the study except for partial dates described in Section [4.1.1.7](#).

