4.1.1.6 Derived Variables

- Change from baseline = value at current time point – baseline value
- Percentage change from baseline = $\left(\frac{\text{value at current time point} - \text{baseline value}}{\text{baseline value}} \right) * 100\%$
- Spot urinary oxalate-to-creatinine ratio = the average of all the spot urinary oxalate-to-creatinine ratio collected at the specific visit.
- Treatment-emergent AE (TEAE) = any AE with an onset date/time on or after administration (including any partial administration) of the first dose of study intervention and until the study completion date from the end of study CRF.
- Body surface area will be calculated using the following formula (DuBois & DuBois, 1916):
$$BSA = (\text{Weight}^{0.425} \times \text{Height}^{0.725}) \times 0.007184;$$
 with weight in kilograms and height in centimeters.
- Body mass index (BMI) will be calculated using the formula: $\text{Weight [kg]} / (\text{Height}^2 [\text{m}^2])$.
- Estimated Glomerular Filtration Rate (eGFR) will be calculated as described in Protocol Section 8.2.6.1.
- Annualized stone event rate will be derived as number of stone events in the exposure period / total number of years exposed.

The number of stone events will be calculated as the number of discrete (non-concurrent) adverse events marked as a Kidney Stone Event on the adverse event CRF. Kidney stone events include renal stone requiring medical intervention, stone passage with or without hematuria, and renal colic requiring medication.

Concurrent events will be defined as events occurring within the same 4-week (28-day) window. For example, renal colic treated with medication on Monday 12 November 2019 followed by stone passage without hematuria on Friday 30 November 2019 is a single (concurrent) stone event (18 days between start and stop of single stone event). Renal colic treated with medication on Monday 12 November 2019 followed by stone passage without hematuria on Wednesday 13 December 2019 is considered two separate stone events (30 days between discrete event one and event two).

- Quality-of-life Questionnaires:

PedsQL

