4.2.2 Main Analytical Approach

The primary analysis of the primary endpoint will be performed for MITT using a restricted maximum likelihood (REML) based MMRM approach with percent change from baseline at scheduled visits (Month 1 – Month 6) as the dependent variable. Analysis will include fixed effects of scheduled visits, baseline spot urinary oxalate-to-creatinine ratio, baseline age and baseline eGFR. Denominator degrees of freedom for the F-test for fixed effects will be estimated using the Kenward-Roger approximation. A compound symmetry (CS) covariance structure will be used to model the within-patient error given the small sample size for this study. The primary estimate is the least square (LS) mean of the percent change from baseline at Month 6. This LS mean will be presented along with corresponding standard errors (SEMs) and 95% confidence intervals (CI). Similar analysis will be performed to estimate the LS mean of the percent change from baseline averaged over Month 3 to Month 6.

Descriptive summary statistics (n, mean, standard deviation, median, minimum, maximum) for MITT population by PH type and by age group (0-<2, 2 - < 6, 6-<9, and 9 - 11 years) will also be provided.

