4.3.1.2.2 Clinical Laboratory Evaluations

Descriptive summaries for safety laboratory assessments will be presented at each visit starting at baseline. Changes from baseline to each post baseline visit will also be presented for continuous outcomes.

Baseline for safety laboratory assessments will be identified as defined in Section 4b.1.1.2 regardless of whether an evaluation was scheduled, retested, or unscheduled. Since laboratory retests can occur for individual parameters, it will be necessary to define the baseline and all subsequent visit-specific laboratory values individually for each parameter.

In the case where below the limit of quantitation (BLQ) results are observed, and the lower limit of quantification (LLOQ) value is known, the BLQ values will be included in the numeric summary as the reported LLOQ value. In for those lab results reported as ‘<x’ where x is numeric value, descriptive summaries will impute x as the lab result.

The following imputation rules will be applied to safety laboratory results where LLOQ value is unknown:

- If the patient has quantifiable concentrations of that analyte from other study visits, BLQ results will be imputed as ½ of the patient’s lowest concentration for that analyte.
- If the patient does NOT have any quantifiable concentrations of that analyte from other study visits, BLQ results will be imputed as ½ of the lowest concentration of that analyte based on all quantifiable results within the patient’s age group.

By visit summary tables will be presented for each category of data separately. Routine clinical laboratory data will include hematology, clinical chemistry, coagulation parameters, and urinalysis.

Shift tables for baseline to maximum and minimum post baseline grades, based on laboratory normal ranges (below lower limit of normal [LLN], normal, above upper limit of normal [ULN]), will be provided for hematology, coagulation, cytokine, and clinical chemistry parameters. This analysis of extreme value shifts (e.g., maximum and minimum post baseline grades) will be based on all post baseline assessments whether scheduled or unscheduled.

Results of urine pregnancy tests (females only) will be presented in a listing only. Anti-drug antibody tests will be handled similarly.

Data listings for all laboratory results will be generated. Where appropriate, abnormal values (e.g., above the upper limit of normal or below the lower limit of normal) will be identified.

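### Spot urine oxalate or creatinine reported below the quantification limit apparently stays out of the primary analysis and the normalisation count, and the count has no LLOQ sensitivity analysis

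*SAP*

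**What the plan says.** - **Visit value.** SAP 4.1.1.6 defines the ratio at a visit as "the average of all the spot urinary oxalate-to-creatinine ratio collected at the specific visit". Protocol 8.1.1 plans four samples per on-treatment visit and six at screening.
- **Baseline.** SAP 4.1.1.2 uses "the average of all available spot urine samples (retest samples will be used if available) collected at screening will be used as baseline value". No rule is given for results below LLOQ.
- **Primary analysis.** SAP 4.2.2 fits an MMRM to percent change in the MITT population. It does not mention results below LLOQ.
- **Imputation.** SAP 4.1.1.3.1, on missing efficacy data, says "No other imputation will be used in the study except for partial dates".
- **Sensitivity analysis.** SAP 4.2.3 repeats the 4.2.2 analyses by "imputing creatinine measurements or urine oxalate values reported as" '<x', where x is the LLOQ. It names both analytes but does not clearly state the value to be substituted.
- **Normalisation endpoint.** SAP 4.3.1.1 counts participants at or below ULN or 1.5 x ULN at any time point through Month 6. It has no LLOQ rule and no LLOQ sensitivity analysis.
- **Safety laboratory data.** SAP 4.3.1.2.2 does have a rule: "the BLQ values will be included in the numeric summary as the reported LLOQ value". Protocol Appendix 2 lists the spot urine parameters in Table 3, apart from the safety tests in Table 4.

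**The concern.** A result reported as '<x' is not missing; it is known to be low. A ratio cannot be computed from it unless a number is put in its place. If the main analysis substitutes nothing, the sample leaves the visit average, and whether it leaves depends on the quantity being estimated. Low oxalate is what the drug is meant to produce, so the samples lost are more often those of children who respond well.

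Participants follow hyperhydration regimens (Protocol 5.3), so dilute urine is to be expected. With four samples per visit and about 20 completers, a few exclusions can change a visit value or a child's classification. The primary estimate at least has a sensitivity analysis; the normalisation count has none.

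**Working it through.** **1. What the text implies.** Imputation is the only thing that distinguishes the LLOQ re-run in SAP 4.2.3 from the main analysis in 4.2.2. If the main analysis already substituted a value, the re-run would have no stated difference from it. With 4.1.1.3.1 added, exclusion is the natural reading. It remains an inference, because no sentence says it. Taken literally, 4.1.1.3.1 also conflicts with 4.2.3 and 4.3.1.2.2, both of which impute.

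**2. One visit by hand.** Protocol inclusion criterion 3 sets 0.12 mol/mol at 7 to 11 years as twice the 95th percentile. Taking ULN as that percentile (an assumption), ULN = 0.12/2 = 0.06 and 1.5 x ULN = 0.09. Assume a baseline of 0.30, two quantified samples at 0.11, and two '<x' samples whose ratio is 0.05 if x is used.

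- Excluded: mean 0.11; change 0.11/0.30 - 1 = -63.3%; not at or below 0.09.
- x: (2 x 0.05 + 2 x 0.11)/4 = 0.08; change -73.3%; at or below 0.09.
- x/2: (2 x 0.025 + 2 x 0.11)/4 = 0.0675; change -77.5%; at or below 0.09.

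**3. Simulation A.** 20,000 children, 6 screening samples and 4 samples at each of 6 visits. Assumed: lognormal ratio and creatinine, baseline median 0.30, median true reduction 50%, within-child log-SD 0.45, ULN 0.06. LLOQ is set so that the stated share of on-treatment oxalate results falls below it, and the same LLOQ applies at screening. Change is the plain mean at Month 6, not the MMRM estimate.

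| Oxalate share below LLOQ | 5% | 10% | 20% | 30% |
|---|---|---|---|---|
| Mean change, true | -44.9% | -45.1% | -44.6% | -44.9% |
| excluded | -44.0% | -43.3% | -41.1% | -39.5% |
| x | -44.4% | -43.9% | -41.4% | -38.9% |
| x/2 | -45.2% | -45.6% | -45.4% | -45.5% |
| Ever <= ULN, true | 8.8% | 9.4% | 8.7% | 8.8% |
| excluded | 7.0% | 6.6% | 5.3% | 4.1% |
| x | 6.6% | 4.2% | 0.9% | 0.1% |
| x/2 | 10.8% | 12.5% | 12.8% | 11.8% |
| Ever <= 1.5 x ULN, true | 29.2% | 28.7% | 28.2% | 28.4% |
| excluded | 27.2% | 24.9% | 21.7% | 20.0% |
| x | 27.9% | 25.1% | 17.1% | 8.5% |
| x/2 | 30.7% | 31.7% | 34.1% | 35.9% |

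Exclusion loses 0.9, 1.8, 3.5 and 5.4 points of mean change. It loses 1.8, 2.8, 3.4 and 4.7 points of the share ever at or below ULN, and 2.0, 3.8, 6.5 and 8.4 points at 1.5 x ULN.

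**4. Stronger response.** With a true mean change of -59%, baseline median 3 x ULN, sample CV 35% and creatinine CV 70%, exclusion gives -57.5/-56/-54% at 10/20/30% below LLOQ, a loss of 1.5, 3 and 5 points. In a close variant (true mean change -58%), the share ever at or below ULN is 55.3%. Exclusion gives 54.7/53.4/51.7%, a loss of 0.6, 1.9 and 3.6 points, and x/2 gives 56.1/57.9/59.6%. At 1-2% below LLOQ, the loss of mean change under any of these assumptions is less than half a point.

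**5. Creatinine.** In simulation A with only creatinine below LLOQ (5/10/20%), exclusion raises the share ever at or below 1.5 x ULN from 29.0/28.6/28.6% to 29.8/30.6/32.6%. Mean change moves by less than 1 point (-45.0/-44.9/-44.9% to -44.8/-44.6/-44.1%), because screening samples are affected as well. With 20% of each analyte below LLOQ, the two effects on the share partly offset: 25.5% against a true 28.6%.

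**The case against.** The strongest case is that this is a gap in wording with a conservative effect. No sentence says '<x' urine results are dropped. The no-imputation sentence sits under missing data and cannot be a literal study-wide ban, because the safety section substitutes values. The SAP Introduction leaves further specifications to the mock TFL, which are not available here. Excluding oxalate works against the drug, no hypothesis is tested, and a sensitivity analysis is already planned. No LLOQ or frequency is given, so the effect could be trivial. A '<x' oxalate is also a concentration, not a ratio: in the stronger-response variant, 31-41% of samples below LLOQ were not among the correspondingly lowest ratios.

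Most of this stands, and it limits the claim. It does not remove it. If the sponsor intends something other than exclusion, the SAP should say so. A conservative error is still an error in the quantity the trial sets out to estimate, and the planned sensitivity analysis does not reach the normalisation count. If 4.2.3 means x, as the safety rule suggests, it is no reliable check: in simulation A at 30% below LLOQ, x is further from the truth than exclusion on every measure in the table.

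A reader might infer that the best responders can never count as normalised. The endpoint is met at any time point, so one evaluable visit is enough; in the stronger-response variant only 0.1/0.6/1.5% of children had no usable visit at 10/20/30% below LLOQ. A reader might also infer that plasma oxalate has no rule. Protocol Table 4 lists it with the safety laboratory tests, so SAP 4.3.1.2.2 may already cover it.

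**Conclusion.** The point holds as an apparent exclusion, not as a stated deletion. As written, SAP 4.1.1.3.1 and 4.2.3 leave '<x' urine samples without a place in the visit average, the primary MMRM or the normalisation count. For oxalate this depends on the outcome and tends to understate the reduction.

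The size rests on the unknown share below LLOQ: negligible at 1-2%, about 1 to 2 points of mean change at 10%, and about 3 to 5 points at 20-30%. The any-time-point share at or below ULN loses up to about 4 to 5 points; at 1.5 x ULN the loss reached about 8 points under one set of assumptions. The response, variance and LLOQ inputs, and the value of ULN, are assumptions.

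The documents do not support a claim that the plan flatters the drug overall: oxalate exclusion works against it, while creatinine exclusion raises the normalisation share. Nor is x/2 a cure for every endpoint. It recovers mean change to within about 1 point but overstates the normalisation share.

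**What to change.** Before database lock:

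1. **SAP 4.1.1.6:** state one rule per analyte, applied alike at baseline and on treatment. Keep '<x' oxalate samples in the primary percent-change analysis, for example at x/2, with x and exclusion as sensitivity analyses.
2. **SAP 4.3.1.1:** report the counts at or below ULN and 1.5 x ULN under exclusion, x and x/2 as a bracket. x/2 should not stand alone here.
3. **Creatinine:** state the rule and report results both with '<x' samples excluded and with a substituted value, since exclusion is itself outcome-dependent.
4. **SAP 4.2.3:** state the value substituted.
5. **SAP 4.1.1.3.1:** reconcile with 4.2.3 and 4.3.1.2.2.
6. **Reporting:** tabulate the number of results below LLOQ by analyte and visit. This shows at once whether the issue matters.
7. **Plasma oxalate:** only confirm whether the 4.3.1.2.2 rule applies.

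The cost is SAP wording, one derivation and a few extra tables, with no new data. The small downside is reliance on a conventional substituted value, which the sensitivity analyses bracket.

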1.1 Objectives, Endpoints, and Estimands

1.1.1 Objectives and Endpoints

Objectives	Endpoints
Primary	

 To assess the efficacy of nedosiran in neonates, infants, and children with PH and relatively intact renal function based upon eGFR and serum creatinine 	
 Percent and absolute change from Baseline to Month 6 in spot urinary oxalate-to-creatinine ratio in PH1, PH2, or PH3 participant subgroups
Secondary	

 To characterize the safety of nedosiran in neonates, infants, and children with PH and relatively intact renal function based upon eGFR and serum creatinine 	
 The incidence and nature of TEAEs and SAEs Change from Baseline in 12-lead ECG, physical examination findings, vital sign assessments, and clinical laboratory tests

 To characterize the PK of nedosiran in neonates, infants, and children with PH and relatively intact renal function based upon eGFR and serum creatinine 	
 Plasma PK parameters for nedosiran and/or its metabolites, including C_{max}, AUC_t and AUC_{∞} (if estimable)

 To assess the efficacy of nedosiran in neonates, infants, and children with PH and relatively intact renal function based upon eGFR and serum creatinine 	
 Percentage of participants with spot urinary oxalate-to-creatinine ratio \leq the ULN or $\leq 1.5 \times$ ULN at any time point through Month 6 in PH1, PH2, or PH3 participant subgroups

 To evaluate the effect of nedosiran on eGFR in neonates, infants, and children with PH and relatively intact renal function based upon eGFR and serum creatinine 	
 Change from Baseline in eGFR at Month 6 (only in participants ≥ 12 Months of age at Screening) in PH1, PH2, or PH3 participant subgroups
Tertiary/Exploratory	

 To assess the effect of nedosiran on plasma oxalate in neonates, infants, and children with PH and relatively intact renal function based upon eGFR and serum creatinine 	
 Percent and absolute change in plasma oxalate over time in PH1, PH2, or PH3 participant subgroups

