1.1.2 Primary Estimand

The primary clinical question of interest is: What is the treatment effect of nedosiran in lowering urinary oxalate excretion (Uox) assessed via percent change from baseline in spot urinary oxalate-to-creatinine ratio at Month 6 in PH1 pediatric participants (birth to 11 years of age) with relatively intact renal function.

For the primary objective, the estimand is defined with five attributes:

- Treatment condition of interest is the monthly nedosiran administration.
- The target population is PH1 pediatric participants (birth to 11 years of age) with relatively intact renal function.
- The endpoint is percent change from baseline at Month 6 in spot urinary oxalate-to-creatinine ratio.
- The intercurrent events (ICEs) include treatment discontinuation for any reasons and will be handled by the treatment policy strategy.

[figure not shown]
Population-level summary is the percent change from baseline at Month 6 estimated by Mixed-effect Model Repeated Measures (MMRM) approach.

Rationale for estimand: The primary estimand assesses the treatment benefit of nedosiran in lowering urinary oxalate-to-creatinine ratio that can be expected in clinical practice, provided that the treatment adherence in the study reflects what would be seen in clinical practice.

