1.2 Study Design

This is a Phase 2, multi-dose (3.5 mg/kg, not to exceed 170 mg), open-label, single-arm uncontrolled multi-center study of nedosiran in pediatric participants (birth to 11 years of age) with genetically confirmed PH1, PH2, or PH3, with relatively intact renal function based upon eGFR and serum creatinine.

Figure 1: Schematic design of trial

2 Statistical Hypotheses

No confirmatory testing will be done in this study.

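### In this single-arm trial the LS-mean 95% CI for absolute change treats the enrolled children's covariates as fixed, so it is too narrow for the population mean

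*SAP*

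**What the plan says.** SAP 1.2 describes an "open-label, single-arm uncontrolled multi-center study of nedosiran in pediatric participants". SAP 1.1.1 gives the primary endpoint as "Percent and absolute change from Baseline to Month 6 in spot urinary oxalate-to-creatinine ratio", by PH type.

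SAP 4.2.2 models percent change over Months 1 to 6: "Analysis will include fixed effects of scheduled visits, baseline spot urinary oxalate-to-creatinine ratio, baseline age and baseline eGFR". On covariance it says: "A compound symmetry (CS) covariance structure will be used to model the within-patient error given the small sample size for this study". Degrees of freedom are Kenward-Roger. On the result it says: "This LS mean will be presented along with corresponding standard errors (SEMs) and 95% confidence intervals (CI".

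SAP 4.2.3 carries the method over: "Similar analyses will be performed for absolute change from baseline at Month 6 and averaged over Month 3 to Month 6". SAP 4.1.1.6 defines the outcome: "Change from baseline = value at current time point – baseline value".

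The estimand in SAP 1.1.2 is written for percent change only: "The target population is PH1 pediatric participants (birth to 11 years of age) with relatively intact renal function". The SAP does not say at which covariate values the LS mean is evaluated, or whether its SE is meant to be conditional on the observed covariates. It describes no variance correction, bootstrap or unadjusted interval.

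**The concern.** In a two-arm comparison, the covariate mean at which both LS means are evaluated cancels from the difference. With one arm nothing cancels. The LS mean depends on which children were enrolled, and the model SE leaves that source of variation out.

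The omission matters most for absolute change. If children respond by a roughly constant percentage, those who start higher fall further in absolute terms, and baseline explains much of the outcome. Entering baseline as a covariate then removes that spread from the SE.

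At stake is the printed precision of one part of the stated primary endpoint. In an uncontrolled, estimation-only trial, the interval is the main statement of uncertainty, and readers will take it as describing children with the disease.

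**Working it through.** **Plan's own figure.** There is none to reproduce: the documents state no SD, R² or coverage, and the sample size has no derivation.

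**Inputs from the documents**
- n: about 20 completers (SAP 5) and a goal of about 15 with PH1 (Protocol 1.1), so n = 15 and 20.
- Spread of baseline: the entry threshold runs from 0.44 mol/mol under 6 months to 0.12 at 7 to 11 years (Protocol 5.1). 0.44/0.12 = 3.7-fold by age alone.
- Spread of response: the only one given is from another study (Protocol 2.2.3.1), a mean maximum reduction in 24-hour Uox of 64%, range 28-100%, in 18 participants. (100 - 28)/3.64 = 19.8, an SD near 20 points. This is a rough proxy: different measure, maximum reduction, single dose.

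**Step 1: the variance.** With complete data and the LS mean taken at the sample-mean covariates (the usual default, assumed here), the Month 6 LS mean equals the sample mean.
- Variance over repeated samples of children: σ²/n.
- What the model SE² estimates: (1 - R²)σ²/n.
- Missing part: R²σ²/n, estimated by b'Sb/n, with b the covariate coefficients and S their sample covariance matrix.

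**Step 2: coverage, normal data.** Coverage = 2F(t₀.₉₇₅ √(1 - R²)) - 1, where F is the t distribution with n - 4 df (intercept and three covariates). Example, n = 15, R² = 0.7: 2.201 × √0.3 = 1.206 on 11 df, giving 74.7%.

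| R² | n = 15 | n = 20 |
|---|---|---|
| 0 | 95.0% | 95.0% |
| 0.3 | 90.7% | 90.5% |
| 0.5 | 85.2% | 84.7% |
| 0.6 | 80.9% | 80.1% |
| 0.7 | 74.7% | 73.7% |
| 0.8 | 65.4% | 64.3% |

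**Step 3: what R² to expect.** Let absolute change be -P × B, with P independent of baseline B, mean p and SD s, and let c be the CV of B. Ignoring visit noise, R² = p²c² / [p²c² + s²(1 + c²)]. Assuming p = 0.5, s = 0.2:
- c = 0.45: 0.0506/(0.0506 + 0.0481) = 0.51
- c = 0.66: 0.1089/(0.1089 + 0.0574) = 0.65

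**Step 4: simulation.** 3,000 trials per scenario, n = 15 and 20; complete-data compound-symmetry model over six visits with the planned covariates, and Satterthwaite in place of Kenward-Roger df. Baseline was a multiple of the age ULN, truncated above 2 × ULN. Assumed, not in the documents: mean and SD of percent reduction, baseline CV 0.45 or 0.66, and per-visit noise 0.2. No infants were simulated, because eGFR is not calculated under 12 months. Month 6 coverage for absolute change:

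| Mean reduction | SD 10 | SD 20 | SD 30 |
|---|---|---|---|
| 40% | 73-79% | 80-86% | 83-89% |
| 50% | 62-72% | 72-81% | 81-87% |
| 64% | 48-58% | 64-76% | 74-82% |

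- R² across these scenarios ran from 0.28 to 0.89.
- Months 3-6 average: about 43-88%.
- One run with infants (n = 20, 50%, SD 20): 68%.
- A separate simulation gave 63-90% at Month 6, so the overall range is about 48-90%.
- Percent change at Month 6, simulated independent of baseline: about 94-95%, R² 0.05 or less.

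**Step 5: how much is skewness.** A plain one-sample t interval for absolute change covered about 90-95%. In one case (n = 15, 50%, SD 20, CV 0.66) the planned interval covered 72.9% and the t interval 91.7%. Of the 22.1-point shortfall, 3.3 points are shared with the t interval and are not due to covariate conditioning.

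**Step 6: after correction.** Adding b'Sb/n to the variance gave about 91-96% on the same scenarios; a visit-only MMRM gave about 91-95%.

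**The case against.** The strongest reply is that the interval is correct for what it conditions on. As a CI for the mean at the observed covariate values it follows ordinary regression practice, and the SAP never says that the LS mean for absolute change targets anything else. The written estimand covers percent change only, and 4.2.3 files absolute change under sensitivity analyses. No test, success threshold or multiplicity rule uses the interval. Protocol 9.4.2 also summarizes absolute change by PH type, and SAP 4.2.2 plans n, mean and SD for the primary endpoint; if 4.2.3 extends those to absolute change, a reader could form a one-sample interval.

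Much of this stands, and it limits the severity. It does not remove the point. Absolute change is in the stated primary endpoint, the only target named anywhere is a population of children, and the printed CI would still be the narrow one.

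Two stronger readings are tempting. A reader might infer one definite coverage figure, such as 65-79%. That range needs R² of about 0.6 to 0.8, and the documents supply neither R² nor the SD and baseline spread behind it. A reader might also infer that the percent-change analysis is equally compromised. Nothing in the documents shows covariates predicting percent response; closed-form coverage of about 91% or 85% there would need R² of 0.3 or 0.5.

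**Conclusion.** Wrong as written for absolute change, if the interval is read as one for the population mean; low to moderate severity. The direction follows from the single-arm design and the specified model, and every absolute-change scenario fell below 95%. The size depends on R²: about 91% coverage at 0.3, 85% at 0.5, 74-75% at 0.7 and 64-65% at 0.8. In width, the planned interval is about √(1 - R²) of the full one before the small df difference: 0.71 at R² 0.5 and 0.55 at 0.7.

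This assumes LS means at the sample-mean covariates, near-complete data and a percent response not strongly tied to baseline. The percent-change CI, the one with a written estimand, is essentially unaffected on the same assumptions.

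**What to change.** In SAP 4.2.3, for absolute change at Month 6 and averaged over Months 3 to 6:

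1. State that the target is the population mean and that the LS mean is evaluated at the sample means of the covariates.
2. Keep that LS mean, but add b'Sb/n to its variance before forming the CI; or report the unadjusted (visit-only) MMRM interval alongside the adjusted one.

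The same correction can go into 4.2.2. It costs little there and changes little unless a covariate predicts percent response.

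Do not rely on a percentile bootstrap over participants at this sample size. In a single-visit check (mean reduction 50%, SD 20, CV 0.3 to 0.8, n = 15 and 20, 1,500 replicates per scenario) it covered 85-91%, below both the b'Sb/n interval (89-95%) and the one-sample t interval (88-93%) in every scenario.

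The cost is a few lines of code and SAP text. The point estimate does not change. The interval for absolute change widens, by about 1/0.71 = 1.4 times at R² 0.5 and 1/0.55 = 1.8 times at R² 0.7. Some shortfall from skewness at small n will remain.
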